#### **Exclusion** criteria

- Under 18 years of age
- Participation by either caregiver in a parenting or stress management intervention in the past six months
- Family does not have a child aged 3–14 years

- Anyone who is unable, even with assistance, to complete the assessment questionnaires
- Unwillingness of either caregiver to give informed consent
- Not fluent in Dinka

Based on the successful implementation of the design in the pilot RCT and RCT in Lebanon, a waitlist control will serve as the comparison group in this study. Participants in the waitlist control group will be given the opportunity to participate in the intervention after the 3-month follow-up assessment has been completed.

This study will involve a waitlist control group for two key reasons:

- 1) While the risk of a nocebo effect among research participants randomized into the control group in waitlist-controlled psychological treatment trials has been raised (Furukawa et al., 2014; Gold et al., 2017; Steinert et al., 2017), there is currently little evidence to show that this is the case for preventative interventions (Gold et al., 2017; Miller, et al., 2023).
- 2) The BeThere intervention has already been shown to be effective among caregivers in Lebanon. Considering the vulnerability of the target population and the lack of existing mental health and psychosocial support services, we do not want to deny control group participants access to the intervention.

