#### **Facilitators**

20 facilitators will be recruited to implement a total of 80 intervention groups, 40 in each arm of the trial. BeThere facilitators must fulfil the following criteria to be accepted into the facilitator training:

- 1) Fluent Dinka speaker
- 2) Preferably from the geographic locations of implementation
- 3) Aged at least 24 years
- 4) At least high school education completed
- 5) At least 2 years of experience implementing psychosocial interventions, preferably with adults, especially parents and caregivers
- 6) Affinity with the core ideas of the intervention regarding parental wellbeing and positive parenting
- 7) Able to commit to attend the full training, all sessions of the intervention, and all supervision meetings
- 8) Respectful and tolerant to different nationalities and religious groups
- 9) Being a parent is highly desirable but not required

Prospective BeThere facilitators will participate in a 6-day training that covers the intervention material as well as key group facilitation skills and competencies. The competency of the trainees will be assessed with standardized competency measurement

<sup>3 While being a parent introduces the risk of bias as facilitators may introduce their own experiences and attitudes about parenting, we have found that intervention participants view facilitators with children as having greater legitimacy to lead sessions on parenting knowledge and skills; in addition, facilitator-parents may have a deeper appreciation for the challenges and stressors that parents face. We make every effort, in training, supervision, and on-site coaching, to ensure that any bias introduced to the sessions by facilitators, whether due to having children or any other source, is minimized.

tools. We will purposefully include more facilitators than we need in the training, with final selection of facilitators taking placed afterwards based on performance in the training. This will also ensure we have individuals who have been trained in the intervention as backup in the case of facilitator dropouts. The 6-day training will be followed by a practice run of the full 9-session intervention, during which the facilitators will receive close support and supervision from trained BeThere supervisors.

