#### Group cohesion

Cohesion among participants in each of the intervention groups will be measured using the 7-item Group Cohesiveness Scale (Wongpakaran et al., 2013). The scale measures how engaged participants feel with each other as a whole in the group, including acceptance, trust, care, and participation.

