#### **Methods**

#### Randomization

960 caregivers will be randomized into the two arms. After caregivers have completed the baseline assessment, families will be randomized to the BeThere intervention or a waitlist control group. Randomization will be at the family level to ensure that caregivers from the same family are not randomized into different arms of the study. BeThere groups will be held separately for women and men, yielding a total of 480 caregivers per arm. As we are running the study in five communities, a block randomization design will be used: the total sample (n=960) will be divided equally across the five communities, resulting in a sample of 192 caregivers per community, randomly allocated to either the experimental or control arm (n=96 per arm). They will then be organized into eight intervention groups of approximately 12 caregivers per group in each arm.

[figure not shown]

Figure 5 Randomization and allocation flowchart

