#### Masking

Given the nature of the study, participants and facilitators will not be masked to group assignment. The research coordinator and BeThere trainer/supervisor will also not be masked to group assignment, as they will be involved in scheduling participants into specific groups. All assessments will be carried out by trained research assistants (see the "Research Assistants" section below for details about their background and training). RAs completing the baseline and follow-up assessments will be masked to group assignment and therefore will not be involved in the randomization process. As we did in the pilot study and trial in Lebanon, the rationale for keeping the RAs masked is explained to participants at each assessment, along with a request that they not reveal their group assignment. RAs will be instructed never to ask any participant to reveal their group assignment, and to gently stop participants from revealing their group assignment if they begin to do so during assessments. Efforts will also be made to minimize interactions between the intervention and research teams during the study and there is no planned contact between the RAs and BeThere facilitators. We will instruct RAs to never discuss any research participant outside of the data collection process, except with the research coordinator, both for confidentiality and to ensure against any possible breach of masking to participant assignment. The RAs will convene at the War Child Bor office during data collection periods, while the BeThere facilitators will be community-based. If a need arises for the facilitators to visit the Bor office, we will ensure that the RAs will not be present during those times. We will assess the level of (un-)masking amongst the RAs at each measurement timepoint. RA masking was accomplished successfully during the pilot study and RCT, and we anticipate no difficulties replicating this in the present study. The principal investigator (PI), co-PIs, and trial statisticians will all be masked to group assignment.

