**Table 5: SPIRIT Flow Chart** 

Tuble 3. SPIRIT Flow C	STUDY PERIOD								
	Enrolment	Enrolment Baseline Midline Endline 3-month Follow-							
TIMEPOINT	-t 1	то	t 1	t 2	t 3				
ENROLMENT:									
Eligibility screen	Х								
Informed consent	Х								
Allocation		х							
INTERVENTIONS:									
BeThere		+							
Waitlist-control		+							
ASSESSMENTS:									
Caregivers :									
Demographics		Х		Х	X				
Parenting		Х		Х	Х				
Caregiver wellbeing		Х	Х	Х	Х				
Caregiver stress		Х	Х	Х	Х				

Caregiver distress	Х	Х	Х	Х
Child wellbeing	Х		Х	Х
Group cohesion	Х	Х	Х	Х
Mechanisms of Action	х	Х	Х	Х
Contamination			Х	
Child :				
Child wellbeing	х		Х	Х
Parenting	Х		Х	Х

All questionnaire data will be gathered using tablets, using the software program Kobo, which allows questionnaires to be completed and uploaded without paper and pencil. Kobo is available free of charge from the Harvard Humanitarian Initiative (https://www.kobotoolbox.org/). Measures will be administered in Dinka to each caregiver and child individually by trained and supervised research assistants.

The 15 research assistants will work together under the direction of the research coordinator during data collection periods. Data collection and the start of the intervention groups will take place in a staggered approach over a five-week period with one location starting each week, outlined in Table 2. We estimate that the total sample size when including index children aged 7–14 will be 1,360 (960 caregivers and 400 children), with an average sample of 272 participants per location.

est. # of partici pants	Week1	Week2	Week3	Week4	Week5	Wk 6	Wk 7	Wk 8	Wk 9	Wk 10	Wk 11	Wk 12	Wk 13		Wk 15
272	Baseline, consent, randomi- zation	Session1	Sesssion2	Session3	Session4	Nidline	\$6	S7	\$8	S9	End line				
272		Baseline, consent, randomi- zation	Session1	Sesssion2	Session3	S4	%55 Midline	\$6	S7	\$8	S9	End line			
272			Baseline, consent, randomi- zation	Session1	Sesssion2	S3	S4	S5 Midline	\$6	\$7	S8	S9	End line		
272				Baseline, consent, randomi- zation	Session1	S2	S3	S4	Midline 55	\$6	S7	S8	S9	End line	
272					Baseline, consent, randomi- zation	S 1	S2	53	54	Midline 55	S6	S7	S8	S9	End line

**Table 6** Baseline, midline, and endline data collection schedule

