We will investigate the mediation process of different aspects of caregiver wellbeing and parenting and, through that, examine how these factors affect child wellbeing, helping us understand how best to achieve downstream effects on child wellbeing through psychological interventions. Some of the pathways of interest are illustrated in Figure 4.

[figure not shown]

[figure not shown]
Figure 6 Primary mediation pathways

If the efficacy analysis shows significant between-group differences in the mediators (caregiver stress, caregiver distress, caregiver psychosocial wellbeing, and parenting), then we will use parametric regression models to:

[figure not shown]
- Test for mediation of the intervention on child wellbeing through caregiver stress
- Test for mediation of the intervention on child wellbeing through caregiver distress
- Test for mediation of the intervention on child wellbeing through caregiver psychosocial wellbeing
- Test for mediation of the intervention on child wellbeing through parenting

Since all the measures are continuous, the indirect effects will be calculated by multiplying relevant pathways and bootstrapping will be used to produce valid standard errors for the indirect effects. All analyses will adjust for baseline measures of the mediators (caregiver stress, caregiver distress, caregiver psychosocial wellbeing, and parenting), the outcome (child wellbeing) and putative measured confounders (e.g., socioeconomic status).

Furthermore, these factors will also be analyzed through three sequential mediation models (Figure 5), to assess how the downstream effect of BeThere on child wellbeing is mediated first through (1) caregiver wellbeing, (2) caregiver distress, and (3) caregiver stress, and then through parenting.

Finally, we will also measure the effect of BeThere on caregiver wellbeing, stress, and distress, as mediated through cohesion among the intervention group (Figure 6).

We will assess for the effect of the BeThere intervention on each one of the multiple continuous mediators with the use of linear regression models. We chose an a priori *p*-value of lower than 0.15 to select the appropriate mediators to include in our final mediation analysis (VanderWeele & Vansteelandt, 2014). Multiple mediators require independence with each other. Therefore, we will test independence by examining partial correlations between our mediators after accounting for treatment allocation.

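### The planned mediation of the BeThere effect through group cohesion is not identified, because cohesion is defined only inside groups that waitlist caregivers do not have at any assessment

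*Protocol*

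**What the plan says.** The Analyses section of the protocol adds one further mediation model to those for child wellbeing: "Finally, we will also measure the effect of BeThere on caregiver wellbeing, stress, and distress, as mediated through cohesion among the intervention group". The same section obtains indirect effects as products of path coefficients, with bootstrap standard errors, and estimates the effect of BeThere on each mediator by linear regression.

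The Group cohesion section defines the mediator: "Cohesion among participants in each of the intervention groups will be measured using the 7-item Group Cohesiveness Scale". It stands under the secondary outcome measures, and the opening of the Outcomes section says that outcome measures are taken from all caregivers in both arms. In Table 5 the row "Group cohesion" is marked for caregivers at baseline, midline, endline and 3-month follow-up, with no restriction by arm.

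On timing, the Randomization section says: "After caregivers have completed the baseline assessment, families will be randomized to the BeThere intervention or a waitlist control group". On the control arm, the text under Exclusion criteria says: "Participants in the waitlist control group will be given the opportunity to participate in the intervention after the 3-month follow-up assessment has been completed".

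Objective 4 is narrower than the analysis. It asks how cohesion among those in the BeThere arm affects their wellbeing and distress.

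The Masking section assigns all assessments to research assistants and adds: "RAs completing the baseline and follow-up assessments will be masked to group assignment". The data collection section has them administer the measures to each person individually.

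**The concern.** The first step of a mediation analysis of a randomised effect is the between-arm difference in the mediator. Here the mediator is how a caregiver experiences a group, and only one arm has groups during the study. No waitlist version of the scale is described. The model as written has nothing to put on the control side of its first path, so the mediated share of the effect, which is what the analysis is meant to deliver, would rest on a convention and not on data.

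Two further points follow. The baseline mark in Table 5 asks all caregivers about groups that have not been formed. And a scale that makes sense only to BeThere participants, given one to one by assistants who are meant not to know the arm, could show them the arm before or between their ratings of parenting and distress.

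**Working it through.** **1. Counts, reproduced from the protocol.** 960 / 5 communities = 192; 192 / 2 = 96 per arm; 96 / 12 = 8 groups; 8 × 5 = 40 groups and 40 × 12 = 480 caregivers per arm. This agrees with "20 facilitators will be recruited to implement a total of 80 intervention groups, 40 in each arm of the trial" in the Facilitators section and with "eight intervention groups of approximately 12 caregivers per group in each arm" in the Randomization section. The planned numbers are used below, without attrition.

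**2. Where cohesion can be rated.** Scheduled cohesion assessments: 960 × 4 = 3,840.

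| Visit | BeThere | Waitlist |
|---|---|---|
| Baseline | 0 of 480 (not yet allocated) | 0 of 480 |
| Midline | 480 | 0 of 480 |
| Endline | 480 | 0 of 480 |
| 3-month follow-up | 480 (group has ended) | 0 of 480 |

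At most 480 × 3 = 1,440 fall where a group exists or has existed: 1,440 / 3,840 = 37.5%.

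**3. The model with waitlist cohesion missing.** Let T be arm, M cohesion and Y the outcome. The product method fits

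- M = α + aT + error
- Y = β + c′T + bM + error
- indirect effect = a × b, with a = mean(M in BeThere) − mean(M in waitlist).

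The second mean has no data. All complete cases have T = 1, so the design matrix of the first equation has rank 1 of 2 and that of the second has rank 2 of 3. The quantities a, a × b and c′ cannot be estimated. Only b, the slope within the BeThere arm, can.

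**4. The model with a constant k filled in for the waitlist arm.** M then varies only among BeThere caregivers, so b is their within-arm slope whatever k is, and

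indirect effect = (mean(M in BeThere) − k) × b.

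Each extra point of k lowers the indirect effect by b and raises the direct effect by the same amount; the total does not move. For illustration, one data set was simulated with 480 per arm. The inputs are assumptions, not protocol figures: cohesion mean 25, SD 5; outcome error SD 1; k from 0 to 35. It gave a BeThere cohesion mean of 24.77, b = 0.0299 and a total effect of 0.249.

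| k | a | Indirect | Direct | Proportion mediated |
|---|---|---|---|---|
| 0 | 24.77 | 0.740 | −0.491 | 297% |
| 7 | 17.77 | 0.531 | −0.282 | 213% |
| 14 | 10.77 | 0.322 | −0.072 | 129% |
| 21 | 3.77 | 0.113 | 0.137 | 45% |
| 25 | −0.23 | −0.007 | 0.256 | −3% |
| 35 | −10.23 | −0.306 | 0.555 | −123% |

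The data are the same in every row. Only the convention for the waitlist arm changes, and it decides both the size and the sign.

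**5. Masking, by reasoning.** At baseline nobody is allocated, so nothing can be revealed. From midline on there are two cases. If only BeThere caregivers receive the scale, its presence in the interview shows the arm. If everyone receives it, a waitlist caregiver who has no group to rate may show it. No separate collector for this scale is described.

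**The case against.** The best defence is that the sentence is loosely worded and that Objective 4 states what is meant: a within-arm question that needs no waitlist values. That stands in part. A reader might infer that Objective 4 cannot be answered at all. It can, as an association, from cohesion data in the BeThere arm. But the Analyses section is the place that fixes the method, and it names an effect of BeThere mediated through cohesion, so the two sections have to be reconciled.

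It may also be said that the waitlist arm has groups, since the protocol counts 40 in each arm. Those groups are assigned but do not meet before the last assessment.

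Three stronger readings are tempting and are not supported:

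- *Any cohesion coefficient would merely recode the arm.* Cohesion varies among BeThere caregivers, so b carries information. What is arbitrary is a, and through it the split into direct and indirect effects. The protocol does not say that controls would be given a constant.
- *The rule to adjust for baseline mediators is broken.* That rule lists its mediators (stress, distress, psychosocial wellbeing and parenting) and takes child wellbeing as the outcome. Cohesion is not listed.
- *Masking is lost.* The instruments are in an appendix that is not shown, so item wording, routing and order are unknown. The Masking section asks participants not to disclose, tells assistants to stop disclosures, and assesses unmasking at each timepoint. These measures do not address leakage through this scale, but they leave it a risk and not an established fact. Caregivers report the primary outcome themselves and know their arm, so assessor masking is only partial protection in any case.

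**Conclusion.** The planned mediation is wrong as written. Its first path has no data for 480 of 960 caregivers, and the indirect effect is either not estimable or set by an arbitrary fill value. The baseline mark for cohesion in Table 5 is an error of schedule affecting all 960 caregivers. The mismatch between the Analyses section and Objective 4 is plain on the text; the Analyses sentence also adds stress, which the objective does not name.

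The identification result rests only on the protocol's definition of cohesion and the timing of the waitlist offer. The simulated figures show the mechanism and do not predict this trial. The unmasking concern is an inference limited to midline, endline and follow-up.

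This should be fixed, but it does not threaten the trial's main result directly: the objective is tertiary, and neither the primary parenting model nor the mediation models for child wellbeing use cohesion.

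**What to change.** - **Analysis.** Replace the cohesion mediation sentence with a within-BeThere-arm analysis: midline cohesion predicting endline wellbeing, distress and stress, adjusted for the baseline value of the outcome, with a random effect for intervention group. Report it as a non-randomised association. Adjust for the midline outcome only as a sensitivity analysis, since that may remove an effect already built up in the early caregiver-wellbeing sessions. Align the outcomes with Objective 4.
- **Schedule.** Delete the baseline and waitlist cohesion assessments from Table 5, and state that the scale applies to the BeThere arm only.
- **Collection.** Have existing staff who do not assess outcomes collect cohesion at a BeThere session, outside the masked interview. Keeping it in the interview for BeThere caregivers alone would itself reveal the arm. Placing it after the outcome scales is only a partial fallback: it protects that visit, but what an assistant learns at midline can carry to endline.

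**Cost.** The change needs new wording, a corrected table row and a small collection task at sessions, and waitlist caregivers answer fewer items. The price is that Objective 4 is reported as an association and not as a mediated effect of randomisation. The collection change has to be in place before the first midline visit, because masking once lost cannot be restored.

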#### Introduction

#### **Background and rationale**

Many interventions aimed at improving parenting in conflict-affected settings have implicitly assumed that sub-optimal parenting is caused by a lack of parenting skills and knowledge (Miller, et al., 2020). However, caregiver stress and mental health challenges due to war exposure can lead to sub-optimal parenting and have been linked to increased rates of child-and caregiver-reported child-abuse (Kadir et al., 2019) and parental rejection and harsh punishment (Sim et al., 2018), while caregivers have been shown to be one of the main perpetrators of child abuse in emergencies (Seddighi et al., 2021). A key contribution to the understanding of (sub-optimal) parenting in conflict has been the family stress model, which has shown that war exposure and daily stressors impact caregiver stress and wellbeing, which in turn affect the quality of parenting, negatively impacting a child's psychosocial wellbeing (Figure 1)(Conger et al., 2010; Masarik & Conger, 2017).

**Figure 1** The family stress model, the conceptual model underlying BeThere

Developed by War Child (Miller, et al., 2020), the BeThere caregiver support intervention is a nine-session preventive group intervention for caregivers of children aged 3–14 affected by armed conflict and forced migration. It takes the family stress model as its conceptual basis, seeking to strengthen parenting by improving the mental health and psychosocial wellbeing of caregivers (Figure 2).

However, within a child—caregiver relationship, it is not only parenting that affects the wellbeing of a child, but the mental health of caregivers has been shown to be directly associated with child mental health among refugee and conflict-affected populations (Betancourt et al., 2015; Feldman et al., 2013; Panter-Brick et al., 2014; Slone & Mann, 2016).

<sup>1 What was known as the Caregiver Support Intervention was rebranded in 2022 by War Child and is now known as BeThere.

Interventions aimed at caregiver mental health and the family context have been shown to improve child-level mental health outcomes and may protect children from developing depression (Kadir et al., 2019; Simenec & Reid, 2022).

**Figure 2** The conceptual basis of BeThere

[figure not shown]

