#### Secondary objectives:

- (2) To evaluate the effects of BeThere on participating caregivers' children using childreported outcomes (an effect that was only assessed through parent-reported child outcomes in the initial trial).
- (3) To conduct a study that is fully-powered to conduct sequential mediation analysis that will allow the research team to confirm the hypothesized (and partially demonstrated in exploratory mediation analyses) mediation pathways of how BeThere contributes to downstream improvements in child wellbeing.

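### The protocol makes mutual independence a condition for multiple mediators, which jointly fitted linear models do not need and its own sequential hypothesis rules out

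*Protocol*

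**What the plan says.** The Analyses section selects mediators by the intervention effect on each one (p below 0.15). It then states: "Multiple mediators require independence with each other". To verify this, "we will test independence by examining partial correlations between our mediators after accounting for treatment allocation". It gives no threshold for dependence and no action if dependence is found.

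Earlier, the same section plans four tests with one mediator each (stress, distress, psychosocial wellbeing, parenting). It adds that "these factors will also be analyzed through three sequential mediation models", each running from one caregiver-state measure to parenting and on to child wellbeing.

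Background and rationale gives the theory: "war exposure and daily stressors impact caregiver stress and wellbeing, which in turn affect the quality of parenting". BeThere is described there as "seeking to strengthen parenting by improving the mental health and psychosocial wellbeing of caregivers". Under Objectives, a secondary objective is "To conduct a study that is fully-powered to conduct sequential mediation analysis", in order to confirm these pathways.

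The section Full structural model covers distress, wellbeing and harsh parenting together, and then also names stress and stress management. It reports a proportion mediated, NIE/(NDE + NIE), and takes female caregivers as the primary mediation population.

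**The concern.** A path from caregiver state to parenting is dependence between mediators given allocation. The plan therefore sets as a condition something that its own secondary hypothesis denies. Distress, wellbeing and stress are also three self-reports by the same caregiver, so independence among them is implausible even without the chain.

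The condition is not needed for the planned models either. In least-squares linear models with the same sample and covariates and all mediators entered together, the total effect equals the direct effect plus the sum of the a × b products, whatever the correlation between mediators.

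What is at stake is the mediation objective. A validity condition that will probably fail, with no stated consequence, leaves the analyst to decide after seeing the data whether to drop mediators or to rely on the one-mediator tests. Those separate effects are the ones that overlap when mediators are correlated.

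**Working it through.** **Inputs.** The protocol gives two-sided alpha 0.05 and 425 caregivers per group, so 850 in all (Power and sample size). The final sample of 960 less 10% attrition is 864. Half of that, 432, is taken here as the number of women, which is an assumption. The protocol gives no correlation between mediators and no figure on this point, so there is no stated result to reproduce. All path sizes below are assumed.

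**Step 1: what the sequential hypothesis implies.** Let X be arm, M1 a caregiver-state mediator, M2 parenting and Y child wellbeing, with unit error SDs:

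- M1 = a1·X + e1
- M2 = a2·X + d·M1 + e2
- Y = c·X + b1·M1 + b2·M2 + e3

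The partial correlation of M1 and M2 given X is d/√(1 + d²). The sequential effect is a1·d·b2. For d = 0.2, 0.4 and 0.6 the partial correlation is 0.196, 0.371 and 0.514. It is zero only at d = 0, where the sequential effect is zero too. Barring an exact cancellation by other shared causes, the condition is met only when the hypothesis is false.

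**Step 2: how often the check would find dependence.** If it is read as a 5% test, the Fisher z approximation gives power = Φ(atanh(r)·√(N − 4) − 1.96). For r = 0.10 and N = 850 this is Φ(0.1003 × 29.09 − 1.96) = Φ(0.958) = 0.83.

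| Partial r | N = 425 | N = 850 |
|---|---|---|
| 0.10 | 54% | 83% |
| 0.15 | 87% | 99% |
| 0.20 | 99% | about 100% |

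With N = 432 and 864 the first row becomes 55% and 84%. Family clustering is ignored throughout.

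**Step 3: does dependence harm the joint model?** Assume a1 = 0.3, a2 = 0.2, b1 = b2 = 0.3, c = 0.1 and d = 0.4.

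- True joint indirect effect: a1·b1 + (a2 + d·a1)·b2 = 0.09 + 0.32 × 0.3 = 0.186.
- True sequential effect: 0.3 × 0.4 × 0.3 = 0.036.

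In 1,000 simulated trials of 850 caregivers, the check rejected independence every time. The mean joint estimates were nevertheless 0.186 and 0.036, equal to the true values.

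**Step 4: what happens with one mediator at a time?** Same values:

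- M1 alone: slope 0.3 + 0.4 × 0.3 = 0.42, so the indirect effect is 0.3 × 0.42 = 0.126.
- M2 alone: slope 0.3 + 0.3 × 0.4/1.16 = 0.403, so the indirect effect is 0.32 × 0.403 = 0.129.
- Sum: 0.255 (simulated mean 0.256) against a true 0.186, a ratio of 0.256/0.186 = 1.38.

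The excess of 0.069 has two parts. The sequential path of 0.036 is counted under both mediators. The other 0.033 (0.129 − 0.096) arises because M1, left out of the M2 model, affects both M2 and Y.

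At d = 0 the separate effects sum to 0.150, which is the true value. At d = 0.6 they sum to 0.309 against a true 0.204, just above the mean estimated total effect of 0.298.

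**The case against.** The strongest reply is that the sentence decides nothing. A reader might infer that following it invalidates the confirmatory model. The protocol does not support that: it says only that partial correlations will be examined, mediators are selected on the intervention effect, and the structural model is not made conditional on the check. Step 3 shows that dependence leaves the joint estimates correct. This part of the objection stands. A threshold or follow-up action could also reasonably be left to the statistical analysis plan.

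The four single-mediator tests are planned whatever the correlations show. Their overlap is therefore not caused by the independence sentence, and deleting the sentence alone would not remove it. This stands too, and it is why the fix must also say how those effects are read.

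Checking dependence has a legitimate use. If caregiver state acts on parenting, the a × b product for caregiver state in the joint model omits its route through parenting. One-at-a-time effects can be added only when mediators do not influence one another. That justifies looking at the correlations but does not make independence a general requirement, and the sentence is not limited to this use. Nor does the text say whether it covers the sequential models.

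A reader might also want a fixed inflation factor. With equal paths and a common correlation r among k mediators, separate effects sum to 1 + (k − 1)r times the joint one, or 1.6 to 2.0 for three mediators at r = 0.3 to 0.5. Neither the equal paths nor those correlations are documented, so this is no estimate for this trial. Proportions summing above 100% would further need a true joint proportion above about 63% (1/1.6) to 50% (1/2.0).

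**Conclusion.** The independence statement is wrong as a general requirement and contradicts the plan's own theory and sequential models. That conclusion rests on the text and on the algebra of linear models, and no assumed path size is needed for it.

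The check would probably find dependence if the hypothesis is true. At a partial correlation of 0.10 the chance is 83–84% with about 850–864 caregivers. It is only 54–55% with about 425–432, roughly the primary female population if half the sample are women. These figures assume a 5% significance test and independent caregivers.

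The possible harm is conditional. It requires that mediators be dropped after a failed check, or that separate indirect effects or proportions mediated be summed or treated as distinct. The simulated 0.256 against 0.186 illustrates the mechanism under assumed paths and does not predict its size here. Mediation is a secondary objective, and the primary parenting comparison is unaffected. The wording should still be corrected before analysis, because it invites an avoidable decision after the data are seen.

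**What to change.** Delete independence as a condition, or limit it to interpreting and summing the separate single-mediator effects in the Analyses section. Then state that:

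- mediators are entered jointly, with the paths from caregiver state to parenting estimated and the residual covariances among the caregiver-state mediators left free;
- the joint indirect effect is the main decomposition, and path-specific effects follow the sequential order;
- single-mediator effects, and proportions mediated derived from them, are not additive;
- partial correlations are reported descriptively and trigger no change of model.

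The cost is a few sentences in the protocol or statistical analysis plan, with no extra data or participants. The downside is wider intervals for the individual indirect effects of highly correlated scales.
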